7.3.2 Serious Adverse Event (SAE) Reporting

7.3.3 Reporting of SAE to IRB

All SAEs occurring on this study will be reported to the IRB according to the IRB policy. The IRB requires immediate reporting of all unexpected and study-related (definite or probable) adverse events. The following procedure will be followed for reporting SAE to the IRB:

- Complete the SAE Cover Sheet (See Appendix C)
- If the event is unexpected AND definitely or probably related to the study, complete the IRB Unexpected, Study-related Adverse Events, Incidents, and Information Reporting Form. This form should be submitted within 24 hours of investigator notification of the event.
- If the event is expected OR possibly or unrelated to the study, only the SAE Cover Sheet will be completed. These events will be reported to the IRB at the time of continuing renewal on the Adverse Event & IND Safety Reporting Cumulative Table.

Forms may also be downloaded from the IRB website at:
http://www.med.cornell.edu/research/for_pol/ins_rev_boa.html

7.3.4 Reporting of SAE to FDA

All SAEs will be reported, whether or not considered causally related to the investigational product, or to the study procedure(s). The investigator is responsible for informing the IRB of the SAE as per section 7.5.2. The reporting period for SAEs is the period immediately following the time that written informed consent is obtained through 90 days after the last dose of durvalumab or until the initiation of alternative anticancer therapy.

The Investigator will inform the FDA, via a MedWatch/AdEERs form, of any serious or unexpected adverse events that occur in accordance with the reporting obligations of 21 CFR 312.32, and will concurrently forward all such reports to AstraZeneca. A copy of the MedWatch/AdEERs report will be faxed to AstraZeneca at the time the event is reported to the FDA. It is the responsibility of the investigator to compile all necessary information and ensure that the FDA receives a report according to the FDA reporting requirement timelines and to ensure that these reports are also submitted to AstraZeneca at the same time.

* A *cover page* should accompany the *MedWatch/AdEERs* form indicating the following:

- “Notification from an Investigator Sponsored Study”
- The investigator IND number assigned by the FDA
- The investigator’s name and address
- The trial name/title and AstraZeneca ISS reference number (ESR-##-#####)

* The investigator will also indicate, either in the SAE report or the cover page, the *causality* of events *in relation to all study medications* and if the SAE is *related to disease progression*, as determined by the principal investigator.

* *Send SAE report and accompanying cover page by way of email to AstraZeneca’s designated mailbox: [contact]*

If a non-serious AE becomes serious, this and other relevant follow-up information will also be provided to AstraZeneca and the FDA.

Serious adverse events that do not require expedited reporting to the FDA still need to be reported to AstraZeneca preferably using the MedDRA coding language for serious adverse events. This information should be reported on a monthly basis and under no circumstance less frequently than quarterly.

7.3.5 Reporting of deaths

All deaths that occur during the study or within the protocol-defined 90-day post-last dose of durvalumab safety follow-up period will be reported as follows:

- Death that is clearly the result of disease progression should be documented but should not be reported as an SAE.
- Where death is not due (or not clearly due) to progression of the disease under study, the AE causing the death will be reported to as a SAE within 24 hours. The report should contain a comment regarding the co-involvement of progression of disease, if appropriate, and should assign main and contributory causes of death.
- Deaths with an unknown cause should always be reported as a SAE.
- Deaths that occur following the protocol-defined 90-day post-last-dose of durvalumab safety follow-up period will be documented, but will not be reported as an SAE.

7.3.6 Other events requiring reporting

7.3.7 Overdose

An overdose is defined as a subject receiving a dose of durvalumab in excess of that specified in the Investigator's Brochure, unless otherwise specified in this protocol.

Any overdose of a study subject with durvalumab, with or without associated AEs/SAEs, is required to be reported within 24 hours of knowledge of the event to AstraZeneca/MedImmune Patient Safety or designee using the designated Safety e-mailbox [contact]. If the overdose results in an AE, the AE will also be recorded as an AE. Overdose does not automatically make an AE serious, but if the consequences of the overdose are serious, for example death or hospitalization, the event is serious and will be recorded and reported as an SAE. There is currently no specific treatment in the event of an overdose of durvalumab. The investigator will use clinical judgment to treat any overdose.

7.3.8 Hepatic function abnormality

Hepatic function abnormality (as defined section 7.1.6) in a study subject, with or without associated clinical manifestations, is required to be reported as "hepatic function abnormal" *within 24 hours of knowledge of the event* to AstraZeneca/MedImmune Patient Safety using the designated Safety e-mailbox, unless a definitive underlying diagnosis for the abnormality (e.g., cholelithiasis or bile duct obstruction) that is unrelated to investigational product has been confirmed.

- If the definitive underlying diagnosis for the abnormality has been established and is unrelated to investigational product, the decision to continue dosing of the study subject will be based on the clinical judgment of the investigator.
- If no definitive underlying diagnosis for the abnormality is established, dosing of the study subject must be interrupted immediately. Follow-up investigations and inquiries will be initiated by the Investigator without delay.

Each reported event of hepatic function abnormality will be followed by the investigator and evaluated by AstraZeneca.

7.3.9 Pregnancy

Maternal exposure

If a patient becomes pregnant during the course of the study, the IPs should be discontinued immediately.

Pregnancy itself is not regarded as an AE unless there is a suspicion that the IP under study may have interfered with the effectiveness of a contraceptive medication. Congenital abnormalities or birth defects and spontaneous miscarriages should be reported and handled as SAEs. Elective abortions without complications should not be handled as AEs. The outcome of all pregnancies (spontaneous miscarriage, elective termination, ectopic pregnancy, normal birth, or congenital abnormality) should be followed up and documented even if the patient was discontinued from the study.

If any pregnancy occurs in the course of the study, then the Investigator or other site personnel should inform the appropriate AstraZeneca representatives within 1 day, ie, immediately, but **no later than 24 hours** of when he or she becomes aware of it.

The designated AstraZeneca representative will work with the Investigator to ensure that all relevant information is provided to the AstraZeneca Patient Safety data entry site within 1 to 5 calendar days for SAEs and within 30 days for all other pregnancies.

The same timelines apply when outcome information is available.

7.3.10 Paternal exposure

Male patients should refrain from fathering a child or donating sperm during the study and for 90 days after the last dose of durvalumab monotherapy.

Pregnancy of the patient's partner is not considered to be an AE. However, the outcome of all pregnancies (spontaneous miscarriage, elective termination, ectopic pregnancy, normal birth, or congenital abnormality) occurring from the date of the first dose until 90 days after the last dose should, if possible, be followed up and documented.

Where a report of pregnancy is received, prior to obtaining information about the pregnancy, the Investigator will obtain the consent of the patient's partner. An IRB approved consent will be obtained prior to use.

7.4 Data Safety Monitoring Plan

Subjects will be carefully monitored and evaluated for adverse events by history, physical examination, and laboratory investigations prior to their scheduled durvalumab infusion and on a monthly basis after surgical resection for 4 months. All toxicities encountered during the study will be evaluated on an ongoing basis according to the NCI Common Toxicity Criteria version 4.0. All study treatment associated adverse events that are serious, at least possibly related and unexpected, and caused subject harm, will be reported to the IRB. Any modifications necessary to ensure subject safety and decisions to continue, or close the trial to accrual are also discussed during these meetings.

If there are 3 or more postoperative deaths in the first 20 patients this would be considered outside of our historical control, and thus the study would be stopped. The Weill Cornell Medical College DSMC will perform data and safety monitoring for this study every 4 months. The Weill Cornell Medical College DSMC will review interim data to evaluate research subject safety, rates of accrual, and efficacy of the experimental intervention. After each evaluation, the Board will provide the principal investigator with recommendations for protocol modification, continuation or termination.

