5.1 Treatment Plan

Patients with biopsy proven NSCLC clinical stages I (tumors > 2 cm), II, and IIIA will be randomly assigned to 2 preoperative cycles of the anti-PD-L-1 antibody durvalumab followed by surgical resection *or* non-ablative stereotactic radiotherapy given concurrently with the first cycle of the anti-PD-L1 antibody followed by an additional cycle of the antibody alone followed by surgical resection. In both arms of the trial, patients will receive adjuvant durvalumab every 4 weeks for a total of 12 cycles. Patients randomized to the antibody alone arm will receive two cycles of durvalumab at a dose of 1.12 g every three weeks. Patients in the radio-immunotherapy arm will also be treated with two cycles of durvalumab (1.12 g q 3 weeks) plus radiotherapy delivered in 3 daily fraction of 8Gy starting concurrently with the first cycle of durvalumab (see trial schema). This delivered non-ablative radiation dose of 24 Gy is equivalent to a biologically effective dose (BED) of 43.2Gy, which is significantly lower than the standard therapeutic dose for ablation of T1-T2 NSCLC (BED>100Gy). The objective is to induce immunogenic cell death, enhance antigen presentation and increase cytotoxic T lymphocyte activity without tumor ablation. This non-ablative dose of radiation is selected based on the results of studies by one of our co-investigators showing that the 8 Gy_x3 regimen resulted in significant immune modulation in preclinical models (24). A research core biopsy for the collection of tumor tissue is suggested but not mandatory. If a tissue biopsy has already been obtained for diagnostic purposes, a core biopsy may be performed for research purposes only to obtain tumor tissue. If a tissue biopsy has not been performed yet for diagnostic purposes, a core biopsy may be performed for diagnosis and tissue will be obtained for research purposes. Tissue from the preoperative core samples and from the resected surgical specimens will be stored for future correlative studies. Although PDL-1 expression is not required for eligibility, preoperative and post-operative tissue will be stored for future determination of PDL-1 expression. All patients will proceed to surgical resection 2-6 weeks after the second cycle of durvalumab regardless of local response assessment and provided that repeat imaging shows no evidence of systemic disease. Postoperative durvalumab will commence 4-12 weeks postoperatively at a fixed dose of 1.5 g every 4 weeks for 12 cycles. Patients receiving adjuvant chemotherapy may commence adjuvant monthly anti-PD-L1 after completing chemotherapy.

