11. STATISTICAL CONSIDERATIONS

11.1 Specific Aims

11.1.1 Primary Aim:

The primary aim of this study is to determine that subablative SBRT at a dose of 8Gyx3 given concurrently with neoadjuvant durvalumab will increase the major pathological response (MPR) proportion from an estimated 15% in Arm 1 (Durva alone) to 35% in Arm 2 (SBRT+Durvalumab). A two-group chi-square test with a 0.20 one-sided significance level will have approximately 83% power to detect the difference between the Arm 1 MPR proportion of 0.15 and the arm 2 MPR proportion of 0.35 when the sample size is 30 in each arm.

11.1.2 Secondary Aim:

The first secondary aim of this study is to demonstrate that the use of durvalumab (with/without radiation) is associated with an improvement in the 2-year disease-free survival (DFS) proportion from 75% (historical control) to approximately 88% with the use of the new antibody. The historical control rate was determined from the DFS rate reported by Strauss et al from CALGB 9633, a US based randomized trial of adjuvant chemotherapy versus observation in patients with pathological stages IB and II NSCLC³⁴. The reported 2-year DFS was 68% in the observation arm and 75% in the chemotherapy arm³⁴. Our institutional data are consistent with these results. Among patients in our database who were assigned a clinical stage, there were 215 patients with clinical stages IB and II some of whom received adjuvant chemotherapy. DFS for these 215 patients is shown in Figure 2 and was 75% at 2 years. We did not use DFS reported from other randomized trials since these were international trials and approximately 20-25% of patients enrolled had stage IIIA disease. In our proposed trial, an improvement in DFS by 13% (75% to 88% at 2 years) represents a 17% relative improvement in DFS; a difference that we believe to be both achievable and clinically meaningful. These results will necessarily lead to larger randomized trials for further confirmation.

Another secondary aim is to compare the clinical response between patients receiving the durvalumab alone (Arm 1) and patients receiving the antibody with radiation (Arm 2). Assuming clinical response proportions of 15% and 35% in Arms 1 and 2, respectively, 95% confidence intervals for the clinical response proportions can be constructed to be within $\pm 12.8\%$ and $\pm 17.1\%$ of the observed clinical response proportions in each arm, respectively.

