11.2 Analysis Plan for Endpoints

11.2.1 Primary Endpoint:

The primary endpoint of the MPR proportion will be calculated for both treatment arms and 80% one-sided confidence intervals will be estimated via binomial proportions. The chi-square test or Fisher's exact test will be used, as appropriate, to compare the MPR proportions between the two arms. We will also generate the odds ratio and a corresponding 95% confidence interval to contrast the difference in MPR proportions between the two arms. Logistic regression will be used to generate the odds ratio and corresponding CI.

11.2.2 Secondary Endpoints:

The first secondary endpoint of 2-year DFS proportion will be calculated for the pooled group of patients (N=60) and a 95% confidence interval will be estimated via binomial proportions. An additional calculation will also be stratified by Arm 1 vs. Arm 2. The chi-square test or binomial exact test, whichever is appropriate, will be used to compare the 2-year DFS proportion in the 60 patients to the historical 2-year DFS proportion of 75%. The chi-square test or Fisher's exact test will be used, as appropriate, to compare the 2-year DFS proportion between the two arms.

The clinical response proportion will be calculated for both treatment arms and 95% confidence intervals will be estimated via binomial proportions. The chi-square test or Fisher's exact test will be used, as appropriate, to compare the clinical response proportions between the two arms.

The safety of durvalumab with and without low dose SBRT in the neoadjuvant setting in NSCLC will be investigated. All AEs in both arms \geq G3 with and without possible or probable attribution to study drug will be tabulated. The frequency of subjects experiencing toxicities will be tabulated for each arm. Toxicities will be assessed and graded according to CTCAE v. 4.0 terminology. Exact 95% confidence intervals around the toxicity proportions will be calculated to assess the precision of the obtained estimates. All analyses will be performed in SAS Version 9.4 (SAS Institute, Inc., Cary, North Carolina) and STATA Version 13.0 (Stata Corporation, College Station, Texas).

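### Does four-monthly DSMC review of efficacy, with no efficacy stopping criterion, undermine the MPR test or the pooled DFS comparison?

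*Combined protocol and SAP*

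**What the plan says.** Section 7.4 states that the DSMC "will perform data and safety monitoring for this study every 4 months", that it "will review interim data to evaluate research subject safety, rates of accrual, and efficacy of the experimental intervention", and that after each review it gives the investigator "recommendations for protocol modification, continuation or termination". The only numerical stopping rule in that section concerns postoperative deaths among the first 20 patients. Neither Section 7.4 nor Section 11 contains an efficacy or futility boundary, a number of looks, or a statement on whether efficacy may close accrual.

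Section 11.1.1 sizes the trial for a single comparison of MPR, 15% against 35%, with 30 patients per arm: "A two-group chi-square test with a 0.20 one-sided significance level will have approximately 83% power". Section 11.2.2 sets out to "compare the 2-year DFS proportion in the 60 patients to the historical 2-year DFS proportion of 75" per cent. No significance level, sidedness or power is given for that DFS test, only a 95% confidence interval.

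On timing, Section 5.1 says "All patients will proceed to surgical resection 2-6 weeks after the second cycle of durvalumab", and Table 1 puts resection on days 36–69. MPR is therefore known about 5–10 weeks after a patient starts, long before 2-year DFS.

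**The concern.** A committee that sees efficacy repeatedly and can recommend termination is, on its face, conducting interim analyses. With no boundary, two things could go wrong.

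- **False positives.** The primary test has a generous one-sided level of 0.20. Reusing that level at each review would inflate the error substantially.
- **Early closure on a good MPR result.** Even a strict threshold would stop some trials near half of the planned enrolment. The pooled DFS comparison, the first secondary aim, would then lose patients, and the MPR difference reported at the stop would be too large because stopping selects favourable results.

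Both matter for a phase II trial whose results are meant to inform larger randomized trials.

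**Working it through.** **Inputs.** From Section 11: MPR 0.15 and 0.35, 30 per arm, one-sided 0.20; DFS 0.75 against 0.88, N=60. From Section 7.4: a review every 4 months. Assumptions, because the documents are silent: 2, 3 or 6 equally spaced analyses in total, counting the final one; an interim stop at one-sided p<0.025; a two-sided 0.05 level for DFS.

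**1. The plan's own power.** The pooled proportion is 0.25. The standard error under no difference is √(2×0.25×0.75/30) = 0.1118. Under the alternative it is √[(0.15×0.85 + 0.35×0.65)/30] = 0.1088. Power = Φ[(0.20 − 0.8416×0.1118)/0.1088] = Φ(0.974) = 0.835, which agrees with the stated 83%. Exact enumeration of the chi-square test gives power 0.850 and actual size 0.210 at a common MPR of 15%.

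**2. No stop for benefit.** This is what Section 11 describes. The test is done once at 30 per arm, so the size stays at 0.210 and the DFS comparison has its 60 patients. Looking at data without acting on it changes neither.

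**3. Assumed interim stop at p<0.025 (chi-square, exact enumeration over both arms' response counts).**

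| Total analyses | Error at 15% vs 15% | Chance of early stop at 15% vs 35% | Mean N at stop | Mean observed difference at stop |
|---|---|---|---|---|
| 2 | 0.213 | 0.254 | 30.0 | 0.391 |
| 3 | 0.213 | 0.343 | 32.0 | 0.395 |
| 6 | 0.219 | 0.485 | 29.3 | 0.416 |

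With Fisher's exact test, which Section 11.2.1 also allows, the chance of an early stop falls to 13%, 22% and 32%.

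**4. DFS power by sample size.** The rule is to reject when the number disease-free reaches the smallest r with P(X≥r | N, 0.75) ≤ 0.025. Power is P(X≥r | N, 0.88).

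- N=60: r=52, power 0.710
- N=40: r=36, power 0.467
- N=36: r=33, power 0.358
- N=30: r=28, power 0.285

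**5. DFS power over all trials, stopped or not.** Average power = P(stop) × power given a stop + [1 − P(stop)] × 0.710.

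- 2 analyses: 0.254×0.285 + 0.746×0.710 = 0.60
- 3 analyses: 0.343×0.396 + 0.657×0.710 = 0.60
- 6 analyses: 0.485×0.313 + 0.515×0.710 = 0.52

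The range 0.3–0.5 applies only to trials that stop with about 30–40 patients.

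**6. Patients already enrolled.** These figures count only patients with an MPR result. If accrual took one year (60/52 = 1.15 per week), a lag of 5–10 weeks would add about 6–12 patients to the DFS set. With 8 added, the averages become 0.66, 0.61 and 0.56.

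**7. Sensitivity to the DFS assumptions.** With one-sided 0.05, power is 0.82 at N=60 and 0.51–0.65 at N=30–40. With the 89% target in Section 1.2 and two-sided 0.05, it is 0.79 and 0.34–0.55.

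**The case for a change.** The strongest case for a change is that the text permits termination after an efficacy review and sets no criterion. The only level stated for MPR is 0.20. If that level were reused at each of 2 to 9 analyses, the error at a 15% null would reach 0.31–0.52 with chi-square. With Fisher it would be 0.16–0.26 across null rates of 15% and 25%. Under a stricter trigger, the MPR difference at a stop would average about twice the true 0.20. One or two sentences would rule this out at almost no cost.

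The arithmetic stands, and so does the observation that the criterion is absent. The inference from it is weaker.

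- Nothing in the plan applies the 0.20 level, or any other level, at a review. Every quantified harm follows from a threshold that has to be supplied from outside.
- DSMC output is a recommendation to the investigator, not an automatic stop. Any operating procedures of the committee lie outside the documents.
- Section 1.4.1 says that a link between pathological response and survival has not been definitively shown in NSCLC, and Section 11.1.2 looks ahead to larger randomized trials. Closing a 60-patient phase II trial early because MPR looks good is not the natural reading.
- The sentence saying that "decisions to continue, or close the trial to accrual are also discussed during these meetings" follows adverse-event reporting and opens with modifications needed for subject safety. It is weak evidence of an intention to stop on efficacy.
- A statement restricting MPR alone would not close the gap. Blinded RECIST response (Section 9.2) comes from the pre-operative scan on days 36–49, no later than resection, and stopping for lack of efficacy would also need to be addressed.

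**Conclusion.** No change to the plan is called for. Section 7.4 leaves out how the committee may use efficacy data, but Section 11 is a complete single-analysis design and is sound when followed as written: one test at one-sided 0.20 with 30 per arm, and DFS in 60 patients. A conventional stopping threshold would add at most about 0.01 to the error (0.210 to 0.213–0.219). The DFS cost, from 0.71 to an average of 0.52–0.60, or 0.56–0.66 with 8 patients already enrolled, arises only if the committee acts on a rule the plan does not contain. It also rests on an assumed number of reviews, an assumed p<0.025 trigger and an assumed two-sided 0.05 DFS level. A sentence of clarification would do no harm, but it would record a policy for a hypothetical action and would not correct any planned analysis. If accrual did close early, analysts would report DFS with the achieved N and its confidence interval, and would note that the MPR estimate came from a trial stopped early.
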